9.0 Response

- 9.1. Normalization of hyperbilirubinemia ($Tbili \leq 1.5 \times ULN$) or at least 50% reduction in peak total bilirubin within 11 days in patients who received PEG-asparaginase
- 9.2. Normalization of hyperbilirubinemia ($Tbili \leq 1.5 \times ULN$) or at least 50% reduction in peak total bilirubin within 7 days in patients who received inotuzumab ozogamicin

10.0 OUTSIDE PHYSICIAN PARTICIPATION DURING TREATMENT

- 10.1 MDACC Physician communication with the outside physician is required prior to the patient returning to the local physician. This will be documented in the patient record.
- 10.2 A letter to the local physician outlining the patient's participation in a clinical trial will request local physician agreement to supervise the patient's care.
- 10.3 Protocol required evaluations outside MDACC will be documented by telephone, fax or e-mail. Fax and/or e-mail will be dated and signed by the MDACC physician, indicating that they have reviewed it.
- 10.4 Changes in drug dose and/or schedule must be discussed with and approved by the MDACC physician investigator, or their representative prior to initiation, and will be documented in the patient record.
- 10.5
- 10.6 Documentation to be provided by the local physician will include drug administration records, progress notes, reports of protocol required laboratory and diagnostic studies and documentation of any hospitalizations.
- 10.7 The home physician will be requested to report to the MDACC physician investigator all life threatening events within 24 hours of documented occurrence.
- 10.8

11.0 STATISTICAL CONSIDERATIONS

This is an open label phase II study to evaluate the efficacy of levocarnitine and vitamin B complex for the treatment of hyperbilirubinemia ($Tbili > 3 \times ULN$) in adult patients with ALL treated with PEG-asparaginase or inotuzumab ozogamicin.

Two cohorts of patients will be enrolled in the study, patients who were previously treated with PEG-asparaginase and patients who were previously treated with inotuzumab. Evaluation for two cohorts of patients will be separated. Up to 39 patients will be enrolled for each cohort. Total sample size is up to 78.

The primary efficacy endpoint is response, which is defined as bilirubin normalization (TBili \leq 1.5 x ULN) or at least a 50% reduction in peak bilirubin level in 11 days for patients previously treated with PEG-asparaginase and bilirubin normalization (TBili \leq 1.5 x ULN) or at least a 50% reduction in peak bilirubin level in 7 days for patients previously treated with inotuzumab after initiation of the study treatment. All patients who receive at least 1 dose of levocarnitine will be assessed for safety. Patients must receive at least 5 consecutive days of levocarnitine to be considered evaluable for response.

Our retrospective data suggested that without any treatment the median time to bilirubin normalization (TBili \leq 1.5 x ULN) or at least a 50% reduction in peak bilirubin level was 21 days for patients previously treated with PEG-asparaginase, and the median time to achieve hyperbilirubinemia normalization (TBili \leq 1.5 x ULN) or at least a 50% reduction in peak bilirubin level was 14 days for patients previously treated with inotuzumab. Assuming that the time to normalization follows exponential distributions, then estimated failure rate (no normalization of grade \geq 3 hyperbilirubinemia or less than 50% reduction in peak total bilirubin) would be 70% at day 11 for patients previously treated with PEG-asparaginase and at day 7 for patients previously treated with inotuzumab, respectively. This corresponding to a response rate of 30%.

With the proposed study treatment, it is expected that the median time to achieve hyperbilirubinemia normalization or at least a 50% reduction in peak total bilirubin will be shortened to 11 days for patients previously treated with PEG-asparaginase, and to 7 days for patients previously treated with inotuzumab. That is corresponding to a 20% increase in response rate (i.e. an increase from 30% to 50%) for each of the cohort of patients.

Simon's two-stage Minimax design³² will be implemented for each cohort of patients. The null hypothesis that the true response rate is 30% will be tested against a one-sided alternative 50%. In the first stage, 19 patients will be accrued. If there are 6 or fewer responses in these 19 patients, the study will be stopped. Otherwise, 20 additional patients will be accrued for a total of 39. The null hypothesis will be rejected if 17 or more responses are observed in 39 patients. This design yields a one-sided type I error rate of 0.05 and power of 80% when the true response rate is 50%. The expected sample size is 25.7 and the probability of early stop is 66.6% under the null hypothesis.

Analysis Plan:

The primary endpoint is bilirubin normalization or at least a 50% reduction in peak total bilirubin in patients treated with levocarnitine and vitamin B complex. Response rates will be estimated along with the 95% confidence interval. Secondary endpoints include tolerability of levocarnitine and vitamin B complex and chemotherapy dose intensity. Descriptive statistics will be used to summarize secondary endpoints. The incidence rates of binary secondary endpoints will be estimated, along with the 95% confidence intervals. The duration of time to hyperbilirubinemia normalization or at least a 50% reduction in peak total bilirubin will be estimated using the Kaplan-Meier method. For exploratory purposes, the time to hyperbilirubinemia normalization or achieving at least a 50% reduction in peak total bilirubin will be compared to historical controls using the Log rank test. Competing risk analysis will be considered in the case that patients died before bilirubin normalization or at least a 50% reduction in peak total bilirubin is achieved.

Data from all subjects who receive any study drug will be included in the safety analyses. Subjects who entered the study but did not take any of the study drug and had this confirmed will not be evaluated for safety. The severity of the toxicities will be graded according to the NCI CTCAE v4.0 whenever possible. We will follow standard reporting guidelines for adverse events. Safety data will be summarized by AE category, severity and frequency. The proportion of patients with AEs will be estimated.

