2.2 Levocarnitine and Vitamin B Complex

2.2.1 Description

Levocarnitine is a naturally occurring amino acid that acts as a carrier molecule in the transport of long-chain fatty acids across the inner mitochondrial membrane. The shuttling of long-chain fatty acids across the mitochondria allows for oxidation and energy production. Levocarnitine is obtained through dietary consumption and is also biosynthesized. The biosynthesis requires lysine, methionine, niacin, vitamin B6, vitamin C, and iron.

Vitamin B complex is a dietary supplement composed of thiamine (B1) 3 mg; riboflavin (B2) 3mg; niacin (B3) 20 mg; pyridoxine HCl (B6) 0.5 mg; cyanocobalamin (B12) 1 mcg; pantothenic acid 5 mg per capsule and may be used for patients with nutritional deficiencies.

2.2.2 Rationale for the use of levocarnitine and vitamin B complex for treatment of hyperbilirubinemia

Treatment with both PEG and INO can result in significant hepatotoxicity. In animal models, levocarnitine has demonstrated efficacy in normalizing liver enzyme elevations seen in asparaginase damaged steatotic liver²³. Furthermore, levocarnitine deficiency has been observed as a risk factor for valproic acid liver toxicity, which is thought to also be caused by impaired mitochondrial β -oxidation²⁴. The combination of levocarnitine and vitamin B complex has only been reported in a retrospective manner for the treatment of PEG-induced hyperbilirubinemia²⁵⁻²⁸, however due to the success in this setting and low side effect profile associated with this intervention, it is warranted to investigate the use of these agents to treat hyperbilirubinemia due to either PEG or INO. Levocarnitine and vitamin B complex will be initiated for Tbili > 3xULN. Initiating treatment earlier can hopefully prevent the severity of hyperbilirubinemia that has been reported with PEG. Furthermore, despite an effort to identify patients at risk of developing hyperbilirubinemia after treatment with PEG, we are unaware of any intervention that has been done to try to prevent this toxicity other than dose reduction or avoidance of the agent altogether.

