6.0 Treatment Plan

6.1 General

All patients will be registered with the Data Management Office PDMS/CORE system.

Treatment with levocarnitine and vitamin B complex will be initiated when total bilirubin is >3xULN. Treatment will consist of IV levocarnitine 50 mg/kg loading dose (maximum 3000 mg) followed by 50 mg/kg/day divided every 6 hours beginning 6 hours after the loading dose was administered. Levocarnitine dose may be increased by 50 mg/kg/day to a maximum of 150 mg/kg/day divided every 6 hours (maximum 3000 mg per dose) if no improvement in total bilirubin after 2 consecutive days of treatment at each dose level. See Table 1 for dosing levels. Treatment will continue until total bilirubin is \leq 1.5 x the upper limit of normal (ULN) or at least a 50% reduction in peak total bilirubin is achieved. If hyperbilirubinemia recurs (Tbili >3xULN), levocarnitine and vitamin B may be reinitiated at the previous dose level and continued until Tbili \leq 1.5 x ULN or at least a 50% reduction in peak total bilirubin is achieved. It is preferred that the patient continue to receive treatment as inpatient. If the treating physician deems patient appropriate for discharge prior to achieving a Tbili of \leq 1.5 ULN or at least a 50% reduction in peak total bilirubin, it is recommended for patient to continue IV levocarnitine as an outpatient. It is recommended for patient to continue IV levocarnitine as an outpatient at the same inpatient dosage divided twice daily (maximum 3000mg per dose). If patient is unable to continue IV levocarnitine as an outpatient, it is recommended the patient receive levocarnitine 990 mg by mouth three times daily until Tbili of \leq 1.5 ULN or at least a 50% reduction in

peak total bilirubin is achieved. Vitamin B complex 1 capsule will be administered by mouth twice daily until Tbili of \leq 1.5 ULN or at least a 50% reduction in peak total bilirubin is achieved. Patients who do not achieve a response within the timeframe of interest may continue to receive protocol medications including levocarnitine and vitamin B complex if there is clinical benefit, and deemed in best interest of the patient by the treating physician.

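### Does leaving the period for 'peak' bilirubin and day 0 of the retrospective medians unstated undermine the primary endpoint or its 30% null?

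*Combined protocol and SAP*

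**What the plan says.** Section 9.0 defines response in the PEG-asparaginase cohort as normalization (total bilirubin no more than 1.5xULN) or "at least 50% reduction in peak total bilirubin within 11 days in patients who received PEG-asparaginase", and gives the inotuzumab cohort the same criterion at 7 days. Section 11.0 (Statistical Considerations) repeats this, "at least a 50% reduction in peak bilirubin level in 11 days for patients previously treated with PEG-asparaginase", and starts the trial's window when study treatment begins. Section 6.1 uses the same criterion to end treatment: normalization "or at least a 50% reduction in peak total bilirubin is achieved".

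The null rate comes from untreated patients: "Our retrospective data suggested that without any treatment the median time to bilirubin normalization" or halving of the peak was 21 days after PEG-asparaginase and 14 days after inotuzumab. With an exponential model, the untreated failure rate "would be 70% at day 11 for patients previously treated with PEG-asparaginase and at day 7 for patients previously treated with inotuzumab", hence a 30% response rate. Each cohort is then tested at 30% against 50% with a two-stage design: stop at 6 or fewer responses in 19, reject at 17 or more in 39. As an exploratory analysis, time to normalization or to "at least a 50% reduction in peak total bilirubin will be compared to historical controls using the Log rank test".

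No section gives the period over which the peak is found, or the starting event for the two retrospective medians.

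**The concern.** A percentage fall needs a reference value, and here the reference is undefined. Take a patient at 8xULN before the first dose, 5xULN at the first dose and 3.5xULN on day 11. The patient responds if the peak is the highest value since bilirubin first exceeded 3xULN, and does not respond if only values from the first dose onward count. The decision boundaries are counts in an open-label study, so one reclassified patient can turn 6 of 19 into 7, or 16 of 39 into 17.

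The null raises a second question. There is no concurrent control, and untreated patients have no treatment start from which to count. If their clock started at another event, such as the dose of the causative drug or the day of the peak, 30% would not be the untreated rate on the trial's own clock. The exploratory log-rank comparison would have the same difficulty.

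The recurrence provision in Section 6.1 looks open as well: "If hyperbilirubinemia recurs (Tbili >3xULN), levocarnitine and vitamin B may be reinitiated at the previous dose level", again until the peak has halved, without saying which episode's peak is meant.

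**Working it through.** **Null rate.** Inputs from Section 11.0: medians m of 21 and 14 days, windows t of 11 and 7 days, exponential times. The response rate by day t is 1 − 2^(−t/m).
- PEG-asparaginase: 1 − 2^(−11/21) = 0.3045
- Inotuzumab: 1 − 2^(−7/14) = 0.2929

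Both round to the plan's 30%. The target medians of 11 and 7 days equal the windows, so the alternative is 1 − 2^(−1) = 0.50, as stated.

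**Design.** The probability of rejection is the sum over x = 7 to 19 of Bin(x; 19, p) × P(Bin(20, p) ≥ 17 − x).
- p = 0.30: rejection 0.0455, early stop 0.6655, expected sample size 25.69
- p = 0.50: rejection 0.8036

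These agree with the plan's 0.05, 66.6%, 25.7 and 80%.

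**Does the period for the peak change the classification?**
- Peak before the first dose (8, then 5 at first dose, then 3.5): 1 − 3.5/8 = 0.5625 over the whole episode, a response; 1 − 3.5/5 = 0.30 from the first dose, no response. The final 3.5xULN is above 1.5xULN, so normalization does not settle it.
- Same values with bilirubin still rising (5 at first dose, then 8, then 3.5): 1 − 3.5/8 = 0.5625 on both readings.

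The readings part only when the highest value precedes the first dose. Section 2.2.2 says "Levocarnitine and vitamin B complex will be initiated for Tbili > 3xULN", with the aim of treating early, so the first pattern is possible but off the intended path. A reading that ignored values after the first dose would fit poorly. Section 6.1 ends ongoing treatment by reference to the peak and allows for bilirubin that does not improve on treatment, so values on treatment must be able to set the peak.

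**Does a delay before treatment bias the null?** Under the plan's exponential model, the rate over the next t days among patients unresolved at delay d is 1 − S(d + t)/S(d) = 1 − 2^(−t/m). It does not depend on d and stays at 30.4% and 29.3%.

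**What if day 0 was a different event?** The documents give no lag, so L is assumed. If the retrospective clock started L days before the point matching the trial's start, the remaining median is m − L and the untreated rate is 1 − 2^(−t/(m − L)):

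| L (days) | PEG-asparaginase rate | Rejection probability | Inotuzumab rate | Rejection probability |
|---|---|---|---|---|
| 0 | 30.4% | 0.052 | 29.3% | 0.037 |
| 1 | 31.7% | 0.073 | 31.1% | 0.063 |
| 3 | 34.5% | 0.141 | 35.7% | 0.177 |
| 5 | 37.9% | 0.263 | 41.7% | 0.436 |

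If instead it started at the peak, L days after the trial's start, no halving can occur in the first L days and the rate is 1 − 2^(−(t − L)/m). For L = 1 to 5 this falls from 28.1% to 18.0% (PEG-asparaginase) and from 25.7% to 9.4% (inotuzumab), which makes the test conservative. The sign of any shift is therefore unknown.

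**What the documents say about alignment.** Section 11.0 states the retrospective and trial criteria in the same terms. It describes retrospective failure in terms of grade 3 or higher hyperbilirubinemia, and Section 2.1 puts the lower limit of grade 3 at 3xULN, the level that starts treatment. It also expects the retrospective medians to shorten to the trial's own windows, which makes sense only on a common clock.

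**The case for a change.** The strongest reply is that identical wording of an undefined term proves nothing. The endpoint cannot be programmed from the text for every patient, the study is open-label, the null has no other support, and a few sentences would settle the matter. As the table shows, a clock mismatch of a few days would matter.

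Part of this stands. The text is incomplete, and the meaning of peak is best recorded before responses are counted. But that is ordinary specification work. Eligibility requires a bilirubin above 3xULN, so values before the first dose exist, and Section 8.4 asks for daily measurement in inpatients. The team that computed the retrospective medians knows their day 0. No stated rule is shown to give a wrong answer, and the figures for a shifted clock rest wholly on an assumed lag.

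Reporting a second response rate with the clock started at first bilirubin above 3xULN would add little. It would count untreated days against a 7- or 11-day window and would have no comparator unless the retrospective clock also started there.

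The recurrence sentence is a separate matter. With a first peak of 12xULN, a recurrence at 4xULN is already 1 − 4/12 = 67% below it, so the wording of Section 6.1 must be reconciled by the sponsor. It governs how long re-treatment lasts, not response within 11 or 7 days of the start of treatment, and no clinical rule is proposed here.

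**Conclusion.** The omission is real, but no change to the plan follows. Taken as the highest value of the episode, peak classifies every patient, and the alternative of counting from the first dose differs only for those whose bilirubin peaked before that dose. The documents give no frequency for that group. The 30% null, the boundaries of 6/19 and 17/39 and the sample size all reproduce and would stay the same under any clarification. The effect on the null is zero if the retrospective series used the same peak and a comparable start, as the wording and the shared 3xULN threshold suggest. It is also zero for treatment delay alone under the exponential model. The conclusion rests on that model and on the retrospective data having been handled as Section 11.0 describes them. If the analysts found that the retrospective clock started at a different event, they should report it as a limit on reading 30% as the untreated rate.

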8.0 Evaluation During Study

- 8.1 Comprehensive metabolic panel (CMP) at least weekly
- 8.2 Concomitant medications
- 8.3 Additional monitoring procedures including but not limited to CMP, fractionated bilirubin, serum albumin, diagnostic imaging, to be completed per institutional guidelines. Additional monitoring not required for study. Failure to perform this will not be considered a protocol deviation or violation.
- 8.4 Fractionated bilirubin daily while inpatient, then per treating physician discretion while outpatient.

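### Levocarnitine stops at response, yet 5 consecutive days are required to be evaluable: as written, early responders leave the primary analysis, and the set behind 6/19 and 17/39 is not settled

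*Combined protocol and SAP*

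**What the plan says.** **Treatment duration (Section 6.1).** Levocarnitine and vitamin B complex are given until total bilirubin is at most 1.5 times "the upper limit of normal (ULN) or at least a 50% reduction in peak total bilirubin is achieved". The section also allows longer treatment, but only for the opposite group: "Patients who do not achieve a response within the timeframe of interest may continue to receive protocol medications".

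**Endpoint (Sections 9.0 and 11.0).** Response uses the same bilirubin criterion, met within 11 days (PEG-asparaginase) or 7 days (inotuzumab). Section 9.0 sets no minimum exposure; for inotuzumab it asks for a "reduction in peak total bilirubin within 7 days in patients who received inotuzumab ozogamicin", or normalization. Section 11.0 starts the clock at first treatment: "in 7 days for patients previously treated with inotuzumab after initiation of the study treatment".

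**Evaluability (Section 11.0).** "Patients must receive at least 5 consecutive days of levocarnitine to be considered evaluable for response". The safety set, by contrast, needs only one dose.

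**Numbers and denominators (Section 11.0).** The cap is given as enrolment: "Up to 39 patients will be enrolled for each cohort". The two-stage rule counts 19 and then 39 patients accrued. The analysis plan describes the primary endpoint in patients treated. No replacement rule is given.

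**Bilirubin monitoring (Section 8.0).** "Fractionated bilirubin daily while inpatient", then at the physician's discretion for outpatients, with "Comprehensive metabolic panel (CMP) at least weekly" throughout.

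**The concern.** A patient whose bilirubin halves on day 3, and who stops levocarnitine then as Section 6.1 directs, is a success under Section 9.0 and not evaluable under Section 11.0. Nothing in the protocol says which prevails. On the literal reading, membership of the primary analysis depends on the outcome: the quickest successes are removed and the response rate is biased downward. The 30% and 50% design rates are cumulative from the start of study treatment, so the stated 80% power does not describe a set from which the first days' responses have been taken out.

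The same rule also removes patients who die, withdraw or stop before 5 days without responding, which biases the rate upward. The documents give neither share, so the net direction is unknown.

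The terms enrolled, accrued, treated and evaluable are not reconciled. If 39 is an enrolment cap and some of those patients are not evaluable, 17 of 39 cannot be applied as written. Two analysts following the text could count different patients and reach different go/no-go decisions in either cohort. In an open-label study, that choice would be made with the responses already known.

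**Working it through.** **1. Inputs (Section 11.0).** Null rate 0.30, alternative 0.50, one-sided. Stage 1: 19 patients, stop if 6 or fewer respond. Stage 2: 20 more, reject if 17 or more of 39 respond. Untreated medians are 21 days (PEG) and 14 days (inotuzumab); target medians are 11 and 7 days; time to response is taken as exponential.

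**2. The plan's own figures.** With X1 ~ Bin(19, p) and X2 ~ Bin(20, p):

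- P(stop early) = P(X1 ≤ 6)
- P(reject) = Σ over x = 7 to 19 of P(X1 = x) · P(X2 ≥ 17 − x)
- Expected N = 19 + 20 · (1 − P(stop early))

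At p = 0.30, early stop is 0.666, type I error 0.0455 and expected N 25.7. At p = 0.50, power is 0.804. These agree with the plan. The design rates also follow from its model: 1 − 2^(−11/21) = 30.4% and 1 − 2^(−7/14) = 29.3% untreated, and 50% at the target medians. The Simon arithmetic is sound.

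**3. Literal reading, no time model.** Let f be the share of all patients dropped as early responders and replaced. The evaluable response rate is (0.50 − f)/(1 − f).

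| f (assumed) | Evaluable rate | Power |
|---|---|---|
| 0 | 50.0% | 80.4% |
| 2% | 49.0% | 76.8% |
| 5% | 47.4% | 70.5% |
| 10% | 44.4% | 57.2% |
| 20% | 37.5% | 24.6% |

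Power is 75% at f = 2.9% and 50% at f = 12.3%.

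**4. Literal reading, time models at the target medians.** Let c be the day before which a response leads to exclusion, and m the median. How 5 consecutive days is counted is not stated, so c = 3, 4 and 5 are all shown.

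- Exponential: f = 1 − 2^(−c/m)
- Lag of L days (assumed): f = 0 if c ≤ L, otherwise 1 − 2^(−(c−L)/(m−L))
- Weibull, shape 2 (assumed): f = 1 − 2^(−(c/m)²)

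Power at c = 3 / 4 / 5:

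| Model | PEG (m = 11) | Inotuzumab (m = 7) |
|---|---|---|
| Exponential | 33.7 / 17.7 / 6.9% | 9.4 / 1.0 / 0.02% |
| Lag 2 days | 64.5 / 43.6 / 22.6% | 48.0 / 12.7 / 0.6% |
| Lag 3 days | 80.4 / 62.1 / 38.1% | 80.4 / 38.1 / 3.7% |
| Weibull, shape 2 | 70.4 / 60.8 / 46.7% | 51.2 / 23.8 / 3.1% |

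Example, PEG, exponential, c = 5: f = 1 − 2^(−5/11) = 0.270; evaluable rate (0.50 − 0.270)/(1 − 0.270) = 31.5%; power 6.9%.

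**5. Without replacement.** Expected evaluable patients out of 39 are 39 · (1 − f). Under the exponential model at c = 3 / 4 / 5 this is 32.3 / 30.3 / 28.5 (PEG) and 29.0 / 26.2 / 23.8 (inotuzumab).

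**6. The other reading.** Early responders count, but a share e of all patients are early non-responders who are dropped and replaced. At a true 30% the evaluable rate is 0.30/(1 − e).

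| e (assumed) | Evaluable rate | Type I error |
|---|---|---|
| 0 | 30.0% | 4.5% |
| 5% | 31.6% | 7.1% |
| 10% | 33.3% | 10.9% |
| 15% | 35.3% | 16.5% |

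**7. Both exclusions together.** At a true 50% the evaluable rate is (0.50 − f)/(1 − f − e), which returns to 50% only when e = f.

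**The case against.** The sponsor probably meant to keep early responders. Section 9.0 sets no minimum exposure, Section 11.0 counts from treatment start and refers to accrued patients, and its Kaplan-Meier analysis of time to response makes little sense with the fastest responders removed. A minimum-exposure rule is often there to avoid calling an under-treated patient a failure. On that reading power remains at least 80.4%. This is a fair account of likely intent, but the evaluability sentence is an unqualified requirement and no other text limits it. Nor does the kinder reading clear the plan, because dropping early non-responders then inflates type I error above the stated 0.05 (step 6). If accrued patients are the denominator, the 5-day sentence has no function.

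The lowest power figures are also open to challenge. The plan uses the exponential only to turn medians into rates at days 11 and 7, and that model puts the most response in the first days. Section 6.1 provides for dose escalation when there is no improvement after 2 days, so some slow starts are expected. This stands: those figures show possible size and are not forecasts. The power figures also assume replacement, which the plan does not state.

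Finally, outpatients need a metabolic panel only weekly, so some may pass day 5 before a response is documented. That share is not given, and inpatient treatment, with daily bilirubin, is the stated preference.

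**Conclusion.** The concern holds. The stopping rule and the evaluability rule conflict for any patient who responds before completing 5 days, and the set for both decision boundaries is unreconciled in both cohorts. This must be fixed because it bears on the primary endpoint and on every go/no-go decision.

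The size cannot be fixed from the documents. On the literal reading with replacement, power at a true 50% ranges from no loss (80.4%, nobody responding before the cut) to very low values under the plan's exponential model; an early-responder share of 12.3% is enough to bring it to 50%. If early responders are kept, power is preserved, but type I error exceeds 5% once 5% of patients are dropped as early non-responders and replaced. The two biases oppose each other, and they cancel at a true 50% only if the two dropped shares happen to be equal.

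**What to change.** In Section 11.0:

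1. State that a patient who meets the response criterion within 11 days (PEG-asparaginase) or 7 days (inotuzumab) of the first dose is evaluable and counts as a responder, whatever the number of levocarnitine days.
2. Name the one set to which 6/19 and 17/39 both apply, and use that term throughout. Preferably this is all patients with at least one dose of levocarnitine, already the safety set, with death, withdrawal or loss before response counted as non-response.
3. Use any 5-day set only as a sensitivity analysis, with early responders retained. If a 5-day set stays primary, item 1 still applies and a replacement rule is needed, reconciled with the cap of 39 per cohort.

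In the named set the existing boundaries give 80.4% power at a true 50% and 4.5% type I error at a true 30%, so the design need not change.

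The cost is two or three sentences, with no added patients or visits and no change to any treatment rule. The downside of the one-dose set is that early drop-outs count as failures: the reported rate may be slightly lower, and the 50% target has to hold with them included.

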5.0 Patient Eligibility

Inclusion Criteria:

1. Patients at least 12 years of age
2. Patients with a diagnosis of ALL who are receiving treatment with PEG-asparaginase or inotuzumab ozogamicin with Tbili >3xULN
3. Signed informed consent.

Exclusion criteria:

1. Pregnant or nursing women
2. Known hypersensitivity to levocarnitine or vitamin B complex

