7.0 Pretreatment evaluation

- 7.1 Informed consent
- 7.2 Baseline comprehensive metabolic panel (CMP)
- 7.3 Concomitant medications within 14 days of enrollment
- 7.4 Urine or serum pregnancy test for women of childbearing potential within 7 days of initiating chemotherapy

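### The 30% null describes patients without any treatment, but the plan neither excludes levocarnitine already given for the episode nor uses concomitant-medication records in the response analysis

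*Combined protocol and SAP*

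**What the plan says.** Section 11.0 (Statistical Considerations) takes the null from institutional retrospective data: "Our retrospective data suggested that without any treatment the median time to bilirubin normalization" or a halving of the peak "was 21 days for patients previously treated with PEG-asparaginase", and "was 14 days for patients previously treated with inotuzumab". With exponential times, the failure rate "would be 70% at day 11 for patients previously treated with PEG-asparaginase and at day 7 for patients previously treated with inotuzumab". The trial then looks for "an increase from 30% to 50" per cent with a Simon two-stage design in each cohort, and there is no concurrent control.

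Response (Sections 9.0 and 11.0) is total bilirubin at or below 1.5 times ULN, or a fall of at least half from peak, within 11 days (PEG-asparaginase) or 7 days (inotuzumab) of starting study treatment. The definition places no condition on what else the patient receives. A patient is evaluable after 5 consecutive days of levocarnitine.

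Section 5.0 has two exclusions: pregnancy or nursing, and "Known hypersensitivity to levocarnitine or vitamin B complex". Section 7.3 collects "Concomitant medications within 14 days of enrollment", and Section 8.2 continues that collection on study. The Analysis Plan does not refer to these records.

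**The concern.** A single-arm comparison with a fixed historical rate is fair only if, apart from the study regimen, trial patients are managed much as the historical patients were, and only if time is counted from a comparable starting point. The plan leaves two gaps.

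- **Levocarnitine already running at entry.** Sections 3.1.5 and 3.2.4 say both agents are commercially available, and Section 2.2.2 cites earlier reports of the combination for PEG-asparaginase hyperbilirubinemia. A patient already on it with bilirubin above 3 times ULN is eligible. The 11- or 7-day clock would start at the first study dose, partway through the same therapy. The peak is not tied to a date either, so part of a 50% fall could come before that dose.
- **Other treatment for hyperbilirubinemia or liver injury.** If it is given before or during the window and bilirubin then falls, the patient counts as a responder to levocarnitine and vitamin B.

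At stake is whether a positive result can be attributed to the study regimen, which is the primary objective in Section 1.1.1.

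**Working it through.** **Inputs from Section 11.0.** Historical medians 21 and 14 days; windows 11 and 7 days; null 30%, alternative 50%; stage 1 of 19 patients, stopping at 6 or fewer responses; 39 in total, rejecting the null at 17 or more.

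**Step 1: the null.** Under an exponential model the response rate by day t is 1 − 2^(−t/median).
- PEG-asparaginase: 1 − 2^(−11/21) = 30.4%.
- Inotuzumab: 1 − 2^(−7/14) = 29.3%.

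Both agree with the stated 30%.

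**Step 2: the design.** With true rate p,

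P(reject) = Σ over x = 7 to 19 of P[Bin(19, p) = x] × P[Bin(20, p) ≥ 17 − x].

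- At p = 0.30: 0.0455, with early-stop probability 0.6655 and expected sample size 19 + 20 × (1 − 0.6655) = 25.7.
- At p = 0.50: 0.8036.

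The plan's figures (0.05, 80%, 66.6%, 25.7) reproduce. The design arithmetic is correct for a 30% null.

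**Step 3: sensitivity to the background rate.** Suppose the study regimen is inert, a share f of patients receives another treatment and responds at rate q, and the rest respond at 30%. The overall rate is 0.30 × (1 − f) + q × f. Both f and q are assumptions; the documents give neither.

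| f | q | Overall rate | P(reject) | P(early stop) |
|---|---|---|---|---|
| 0 | – | 0.30 | 0.0455 | 0.666 |
| 20% | 40% | 0.24 + 0.08 = 0.32 | 0.0787 | 0.593 |
| 20% | 50% | 0.24 + 0.10 = 0.34 | 0.1261 | 0.518 |

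A shift of 2 to 4 points roughly doubles to triples the false-positive rate. The table concerns other treatment only. It does not model levocarnitine already running at entry.

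**Step 4: cost of making a stricter count decisive.** Suppose the true rate is 50%, and a share f of patients, independently of response, is reclassified as non-responders. The stricter rate is 0.50 × (1 − f).
- f = 10%: rate 0.45, power 0.599.
- f = 20%: rate 0.40, power 0.356.

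These apply the stricter count at both stages. If stage 1 uses the ordinary count, power is 0.618 and 0.377. The planned power is 0.80.

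**The case against.** The strongest reply is that there may be little competing treatment to worry about. Section 2.1 contrasts hepatotoxicity with other asparaginase toxicities precisely because it has no direct supportive treatment, and Section 2.2.2 knows of nothing to prevent it beyond reducing or avoiding the drug. This stands, and it limits the likely size of the problem for PEG-asparaginase. It does not address inotuzumab or levocarnitine used off study, and it sets no rule.

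Second, the historical patients may simply have had no levocarnitine while ordinary care continued. If trial patients receive the same ordinary care, that care introduces no bias. The wording allows this reading, which is a reason to state what those patients received.

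Third, prior use is possible under the text but not shown. Section 6.1 describes treatment starting once bilirubin passes 3 times ULN, which is also the entry threshold, so the protocol seems to envisage starting on study. A pre-treated patient still above that level has not yet recovered on the drug, so the direction of bias is unclear. For that patient the issue is the starting point of the clock, not attribution to another agent.

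A reader might infer that the trial's type I error really is 8% to 13%, or that a positive result could not be credited to the regimen at all. The documents support neither: they do not show that co-treatment will be given, how often, or that it works.

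**Conclusion.** The point holds as a gap that is cheap to close. The null is described as coming from patients without any treatment. The eligibility criteria admit patients already on levocarnitine for the episode, and the response analysis ignores what else is given. The size of any bias is unknown. The 7.9% to 12.6% error range is conditional on a background rate of 32% to 34%, on an inert regimen, and on a 30% rate in patients without other treatment.

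A reader might also infer that efficacy should be claimed only if a stricter count succeeds too. Step 4 argues against that: with a truly active regimen, power would fall from 80% to about 60% if 10% of patients are reclassified, and to about 36% if 20% are. The sample size and the 6/19 and 17/39 boundaries need no change.

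**What to change.** 1. Add to Section 5.0 an exclusion for patients who received levocarnitine for the current hyperbilirubinemia episode before the first study dose.
2. Keep the primary analysis and both decision boundaries as they are. Add to the Analysis Plan one sensitivity response rate with 95% CI per cohort, in which patients who are on, or start, another treatment given for hyperbilirubinemia or liver injury before response count as non-responders. To support it, record indication and start date under Sections 7.3 and 8.2. Set the rule before data are reviewed, since the study is open-label. Report the result without making it a second condition for success.
3. State in Section 11.0 what bilirubin-directed treatment, if any, the retrospective patients received.

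The cost is a few pre-treated patients not enrolled, two extra fields per relevant medication, and one more tabulation. None of this restricts the care patients may receive on study.
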